### 17.2.2 Neutralization study

Pre-Study Preparation	Neutralization day	
	At least 7 Day Restriction Period	Neutralization day Abdominal Region
Recruit subjects	Initiation of consenting process	Complete Treatment Inclusion/ Exclusion Criteria form
Prepare subject kits	Review study ICF and Inclusion/ Exclusion Criteria	Visual skin assessment (abdominal region)
	Review subject instructions	Mark test areas
	Subject signs ICF	Apply test products
	Visual skin assessment (abdominal and groin regions) and Inclusion/ Exclusion Criteria	Visual skin assessment, within 30 seconds post-prep sample
	Dispense subject kits	Count Neutralization Day plates
	Schedule for clipping/re-clipping, if needed, approximately 48-96 hours prior to neutralization day	

### 17.3 Abdomen and Groin Diagram

#### 17.4 Randomization Scheme Example

The randomization will be provided in a separate document.

Randomization number	Body Area	Product Left Side	Product Right Side	Site 1	Site 2	Site 3	Site 4

**[name], Resident Dermatologist**

**[contact] (work)**

**[contact] (home)**

## **17.6 Treatment Application Instructions**

### **Investigational Product: Treatment A (Project X 26 ml)**

#### Treatment Site Application Instructions – Abdomen

1. Peel open package and remove swabstick – do not touch swab.
2. Hold the swabstick with swab down.
3. Press down the antiseptic reservoir to release the antiseptic to the swab.
4. Wet the swab by repeated blotting against the treatment area until antiseptic is visible on the skin.
5. Thoroughly wet the treatment area with antiseptic using gentle back-and-forth strokes.
6. Repeat steps 4 & 5 for **30 seconds**
7. Do not apply swab beyond borders of marked skin areas by more than one swab width.
8. Allow antiseptic to completely dry (minimum of 3 minutes).
9. Do not blot or wipe dry

#### Treatment Site Application Instructions – Groin

1. Peel open package and remove swabstick – do not touch swab.
2. Hold the swabstick with swab down.
3. Press down the antiseptic reservoir to release the antiseptic to the swab.
4. Wet the swab by repeated blotting against the treatment area until antiseptic is visible on the skin.
5. Thoroughly wet the treatment area with antiseptic using gentle back-and-forth strokes.
6. Repeat steps 4 & 5 for **2 minutes**
7. Do not apply swab beyond borders of marked skin areas by more than one swab width.
8. Allow antiseptic to completely dry (minimum of 3 minutes).
9. Do not blot or wipe dry.

### **Investigational Product: Treatment B (Project X 5.1 ml)**

#### Treatment Site Application Instructions – Abdomen

1. Peel open package and remove swabstick – do not touch swab.
2. Hold the swabstick with swab down.
3. Press down the antiseptic reservoir to release the antiseptic to the swab.
4. Wet the swab by repeated blotting against the treatment area until antiseptic is visible on the skin.
5. Thoroughly wet the treatment area with antiseptic using gentle back-and-forth strokes.
6. Repeat steps 4 & 5 for **30 seconds**
7. Do not apply swab beyond borders of marked skin areas by more than one swab width.
8. Allow antiseptic to completely dry (30 seconds).

9. Do not blot or wipe dry.

**Treatment Site Application Instructions – Groin**

1. Peel open package and remove swabstick – do not touch swab.
2. Hold the swabstick with swab down.
3. Press down the antiseptic reservoir to release the antiseptic to the swab.
4. Wet the swab by repeated blotting against the treatment area until antiseptic is visible on the skin.
5. Thoroughly wet the treatment area with antiseptic using gentle back-and-forth strokes.
6. Repeat steps 4 & 5 for **2 minutes**
7. Do not apply swab beyond borders of marked skin areas by more than one swab width.
8. Allow antiseptic to completely dry (90 seconds).
9. Do not blot or wipe dry.

**Positive Control: Treatment C (Prevantics® Maxi Swabstick)**

**Treatment Site Application Instructions – Abdomen**

1. Peel open package and remove swabstick – do not touch swab.
2. Place one flat side of the foam tip within the pre-measured treatment area, and prep with back-and-forth repeated strokes for 15 seconds.
3. Turn the Maxi-swabstick over and repeat the procedure for 15 seconds.
4. Do not apply swab beyond borders of marked skin areas by more than one swab width.
5. Allow the area to completely air-dry; approximately 30 seconds.
6. Do not blot or wipe dry.

**Treatment Site Application Instructions – Groin**

1. Peel open package and remove swabstick – do not touch swab.
2. Place one flat side of the foam tip within the pre-measured treatment area, and prep with back-and-forth repeated strokes for 60 seconds.
3. Turn the Maxi-swabstick over and repeat the procedure for 60 seconds
4. Do not apply swab beyond borders of marked skin areas by more than one swab width.
5. Allow the area to completely air-dry; approximately 90 seconds.
6. Do not blot or wipe dry.

## 17.7 Procedure for Neutralization Validation

### 17.7.1 Background

The sampling solution, SSF++ is a buffered detergent solution that is commonly used in studies where microbial sampling of skin is conducted. Neutralizers have been added to inactivate the antimicrobial, CHG, present in test treatments. The effectiveness and toxicity of this neutralizer system must be assessed to demonstrate that there is no effect on the growth of microorganisms and that the active ingredient is inactivated.

The density of normal human skin flora generally ranges from  $10^2$  to  $10^5$  CFU/cm^2 depending on the body site. However, since significant neutralizer or toxic effects are more easily detected at a lower cell density, the efficacy and toxicity of this neutralizer system will be assessed against a lower bacterial concentration.

This is a test where the study materials are applied to the abdomen and the treated areas will be sampled. After sampling, *Staphylococcus epidermidis*, a selected representative of normal skin flora will be added into a portion of each sample. Each sample will then be processed using procedures in accordance with ASTM E1054-08(2013). Two samples will be taken from each treatment area whereas one sample will be processed using a methicillin-sensitive *Staphylococcus epidermidis* (MSSE) (ATCC 12228) strain and the remaining sample will be processed using methicillin-resistant *Staphylococcus epidermidis* (MRSE) (ATCC 51625) strain of the test organism.

### 17.7.2 Objective

This control assay will determine the ability of the SSF++ to completely neutralize the active ingredients in the test treatments by recovering and quantifying microorganism populations on agar media and is appropriate for antimicrobial agents that can be chemically inactivated or diluted to sub-inhibitory levels. Each test will be performed in triplicate.

### 17.7.3 Subject Entry Criteria

Six subjects will be used for the neutralization validation required for this study. Each subject must meet the inclusion and exclusion criteria described in Sections 4.1 and 4.2.

No minimum bacterial count is required and the washout period is only necessary for 7 days (not 14 days). The subjects will be asked to provide information on demographics and inclusion/exclusion criteria and sign the ICF before beginning the 7-day washout period. When the subjects return for clipping/re-clipping or to begin their participation in the study they will again be asked to provide information relative to inclusion/exclusion criteria.

If they meet all inclusion/exclusion criteria, they may be enrolled.

- At washout subjects will be assigned numbers starting with 01 to 06
- At Neutralization day subjects will be assigned numbers with 01 and the letter "N": N01

The test article and active control will be applied to the abdomen regions so that three applications are performed for each treatment using bilateral application. The treatments per subject will be randomized. One treatment area will be located on one side of the body and the remaining treatment area on the other side. Each treatment site will have two sampling sites.

### 17.7.4 Test Organism

The test organisms for this study are:

- Methicillin-resistant *Staphylococcus epidermidis* (MRSE), ATCC 51625
- Methicillin-sensitive *Staphylococcus epidermidis* (MSSE), ATCC 12228

### **17.7.5 Study Products**

See [section 3.4](#) of the protocol.

### **17.7.6 Materials, Supplies and Equipment**

See [section 3.4.3](#) of the Protocol. In addition, 70% IPA swabs.

### **17.7.7 In-vivo Test Procedures**

Preparation of Test Area and Post-Prep Sampling: Neutralization samples will be taken from the abdomen. The subject number, location of the prep application, location of the sites sampled within the prep area, and the time of sample collection will be documented on the CRF. The subject will be treated with the study product based on the following:

- For each side of the body, mark the abdominal test areas using the corresponding sterile template per study material. The 1.5" x 5.0" (3.81 cm x 12.7 cm) area will be delineated with each containing two 1" x 1" (2.54 cm x 2.54 cm) sampling sites (one each will be used for each test organism).
- After the test areas are marked, each area will be processed using three 70% IPA swabs for a total of one minute to prepare the site; the areas will be allowed to dry. This step is to prepare the skin for the neutralization test.
- Subjects participating in the neutralization portion of the study will be randomized using a randomization schedule which will be provided in a separate document.
- Prep the test areas with the appropriate treatment according to the randomization schedule and the instructions provided in [Appendix 17.6](#), (using groin treatment application procedures).
- Using the scrub cup technique at approximately 30 seconds post-prep, begin collecting samples from each site using SSF++. This technique is described in [Section 5.2.1](#). For the two sites within each area; the samples will be collected simultaneously by two technicians.

### **17.7.8 In vitro Test Procedures**

#### **17.7.8.1 Inoculum Preparation**

One day prior to beginning the neutralization assay, the test organisms from a working stock culture slant or plate will be inoculated onto TSA plates. The plates will be incubated for  $24 \pm 4$  hours at  $35^\circ \pm 2^\circ\text{C}$ . Immediately prior to initiating the neutralization assay, an inoculum suspension for each test organism will be prepared in PBW solution from the overnight culture on the TSA plate, and the concentration adjusted to approximately  $10^8 - 10^9$  CFU/ml. Bacterial suspension will be further diluted with PBW to achieve an appropriate concentration (approximately  $10^4$  CFU/ml) for inoculation of the test samples. The density of the test inocula will be verified by direct plating at the beginning and end of the study.

#### **17.7.8.2 Test**

(Note – the reference to test product applies to both the investigational products and the active control; all procedures outlined, where applicable will employ both products. In addition, using two samples taken within each treatment area; all procedures, as applicable will be performed using one sample for each of the two test organisms.)

#### **17.7.8.2.1 Neutralizer effectiveness (Test 1)**

- a) Out of the 6.0 mL aliquot of sampling solution taken from the volunteer, 5.0 mL will be transferred to a new sterile tube and inoculated with the challenge microorganism so that the final concentration will equal 30 – 100 CFU/ml of the challenge microorganism (the prepared inoculum will be diluted using PBW to achieve the desired concentration, a 0.1 mL aliquot from the 10^-4 dilution will be used).
- b) Within one min after the addition of the challenge microorganism, the microorganisms will be enumerated by standard microbiological methods extant in the laboratory.
- c) Triplicate 0.75 mL aliquots will be removed and plated using TSA+N pour plates.
- d) After 30 minutes, the microorganisms will be enumerated a second time using the same procedures.
- e) This procedure will be repeated two times for a total of three replicates per test product per time point.

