#### 17.7.10 Interpretation of data

- a) The number of surviving challenge microorganisms for each replicate from each test will be average count of the three plates.
- b) The number of survivor values will be transformed to  $\log_{10}$ .
- c) The number of survivors ( $\log_{10}$ ) from each test (1, 2, and 4) will be compared to the test microorganism viability population (Test 3).
- d) Neutralization aspects of the SSF++ will be considered adequate if the mean  $\log_{10}$  CFU/ml of Test 1 is not more than 0.20  $\log_{10}$  less than the mean  $\log_{10}$  CFU/ml of Test 3 (Mean  $\log_{10}$  CFU/ml from Test 4 – Mean  $\log_{10}$  CFU/ml from Test 1 using corresponding time points).
- e) The SSF++ will be considered non-toxic if the mean  $\log_{10}$  CFU/ml of Test 2 is not more than 0.20  $\log_{10}$  less than the mean  $\log_{10}$  CFU/ml of Test 3 (Mean  $\log_{10}$  CFU/ml from Test 3 – Mean  $\log_{10}$  CFU/ml from Test 2 using corresponding time points).
- f) The mean  $\log_{10}$  CFU/ml from Test 4 must be at least 0.20  $\log_{10}$  less than the mean  $\log_{10}$  CFU/ml of Test 3.
- g) The amount of CFU added for each aspect must be confirmed to yield a final suspension containing 30-100 CFU/ml (validated in test 3).
- h) The absence of growth controls must be negative for growth.

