#### 17.7.11 Controls

Absence of growth control:

Triplicate plates of TSA and TSA+N used will be incubated with the test. In addition, triplicate 1.0 ml aliquots of SSF++ and PBW will be plated using TSA. All plates will be incubated with the test.

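### The neutralizer-effectiveness test has no uninoculated control of the scrubbed skin fluid, so residual native flora could help a partial neutralization failure pass

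*Combined protocol and SAP*

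**What the plan says.** Section 17.7.7 has the abdominal area wiped with three 70% IPA swabs for one minute in total. Its stated purpose is general: "This step is to prepare the skin for the neutralization test". Product is then applied by the groin procedure (two minutes), and the skin is scrubbed with SSF++ about 30 seconds after the prep.

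For Test 1, section 17.7.8.2.1 states: "Out of the 6.0 mL aliquot of sampling solution taken from the volunteer, 5.0 mL will be transferred to a new sterile tube". The tube is inoculated "so that the final concentration will equal 30 – 100 CFU/ml of the challenge microorganism". Plating is within one minute and again at 30 minutes: "Triplicate 0.75 mL aliquots will be removed and plated using TSA+N pour plates". Section 3.4.3 lists only Tween 80 and lecithin as additions to TSA+N, so the agar is not selective. Section 17.7.1 describes the challenge species as representative of normal skin flora.

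Test 3, the comparator, is the same challenge in PBW (17.7.8.2.3). The rule in 17.7.10 d) begins "Neutralization aspects of the SSF++ will be considered adequate if the mean" and, in its wording, allows Test 1 to fall at most 0.20 log10 below Test 3. There is no upper limit.

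The absence-of-growth controls in 17.7.11 are blank TSA and TSA+N plates plus unused fluids: "In addition, triplicate 1.0 ml aliquots of SSF++ and PBW will be plated using TSA". None is fluid from a subject. Section 17.7.3 sets no minimum bacterial count for these subjects, and no count is taken after the wipe.

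**The concern.** Test 1 is meant to show that product carried into the sampling fluid no longer kills. It does so by asking whether a small known challenge is recovered. The fluid comes from living skin, the challenge is a skin organism, and nothing separates added from native colonies. Native colonies therefore enter Test 1 but not Test 3. Because the rule limits only a shortfall, they can offset a real loss of challenge and can never cause a failure.

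Item g) of 17.7.10 does not help, since it confirms the challenge level only in Test 3, where no native flora is present.

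If a partial failure passed, product could go on killing in main-study tubes during the 30 minutes that section 5.2.2 allows before plating. That would lower post-treatment counts, which feed the 0.5 log10 non-inferiority comparison and the 6-hour comparison with baseline (sections 2.1 and 9.3.1).

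**Working it through.** **Inputs.** Cup area 3.80 cm2 (3.4.3); scrub fluid 6 ml (5.2.2); challenge C = 30-100 CFU/ml and inoculum volume 0.1 mL into 5.0 mL (17.7.8.2.1); inoculum about 10^4 CFU/ml (17.7.8.1); limit 0.20 log10 (17.7.10 d). Residual flora on the skin, 10^r CFU/cm2, is an assumption shown over a range.

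**1. The plan's challenge level.** 10^4 x 0.1 / 5.1 = 196 CFU/ml, which does not reproduce 30-100. Reaching that range needs an inoculum of 30 x 5.1 / 0.1 = 1,530 to 100 x 5.1 / 0.1 = 5,100 CFU/ml. Item g) of 17.7.10 requires 30-100 to be confirmed, so I use that range and show 196 as a check.

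**2. Pass threshold.** 10^-0.20 = 0.631, so Test 1 must reach 63% of Test 3.

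**3. Native flora in the tube.** b = 3.80 x 10^r / 6 CFU/ml: 2.0 at r = 0.5, 6.3 at r = 1.0, 20.0 at r = 1.5. The 2% dilution by the inoculum is ignored.

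**4. True challenge recovery s needed to pass**, under two bounding assumptions:
- Native cells killed at the same rate as the challenge: s(C + b)/C >= 0.631, so s >= 0.631 x C/(C + b).
- Native cells unaffected: (sC + b)/C >= 0.631, so s >= 0.631 - b/C, with a floor of 0.

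| Residual flora, log10/cm2 | Killed equally, C = 30 / 65 / 100 | Unaffected, C = 30 / 65 / 100 |
|---|---|---|
| none | 63 / 63 / 63% | 63 / 63 / 63% |
| 0.5 | 59 / 61 / 62% | 56 / 60 / 61% |
| 1.0 | 52 / 57.5 / 59% | 42 / 53 / 57% |
| 1.5 | 38 / 48 / 53% | 0 / 32 / 43% |

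Example, r = 1.0 and C = 30: equal kill gives 0.631 x 30/36.3 = 52%; unaffected gives 0.631 - 6.3/30 = 42%.

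At C = 196 the needed recovery is 61% to 60% at r = 1.0 and 57% to 53% at r = 1.5, so the literal inoculum would shrink the problem.

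**5. On the log scale.** Under equal kill, the extra hidden loss is log10((C + b)/C). For C from 100 down to 30 this is 0.03 to 0.08 at r = 1.0 and 0.08 to 0.22 at r = 1.5.

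**6. Chance of a false pass.** A Poisson simulation used three replicates of three 0.75 mL plates, C = 65 and true recovery 50%. The test passes 0.2% of the time with no native colonies counted, 12% with 5 CFU/ml, 68% with 10 and about 100% with 20. These are native cells still alive at plating. Under equal kill, the 6.3 CFU/ml of r = 1.0 becomes 6.3 x 0.50 = 3.2, which lies between the 0.2% and 12% results.

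**The case against.** The plan already works to remove native flora. A one-minute alcohol wipe is followed by a two-minute application of CHG and alcohol, and these subjects are not selected for high counts. Residuals of 1.0 or 1.5 log10 are assumptions. From a start of 3.11 log10 (the main-study minimum, used only for scale), 1.5 log10 remaining would mean that wipe and product together removed about 1.6 log10. This stands as a limit on size. It does not close the gap, because nothing verifies the removal.

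Product that escapes neutralization would also act on native cells. This stands too. A reader might take the 0% entry to mean that complete neutralization failure could pass. That would need every native cell to survive in a tube where every added cell dies, and no document supports it. Partial failure is the plausible case.

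A reader might also infer a bias toward product A, since 26 ml is used on the same marked area as 5.1 ml of product C. The documents do not support that step. Section 17.6 defines application of A by time and visible wetness within marked borders, not by volume deposited. All three products have the same stated CHG strength, and no carry-over amounts are given. For B against C the volumes are equal. Only a difference between products in undetected kill would shift the non-inferiority contrast.

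**Conclusion.** The gap is certain: no uninoculated fluid from treated skin is plated, and the rule lets native colonies only help. Its effect is unknown, because the plan does not measure residual flora. At 1.0 log10 CFU/cm2, the needed recovery falls from 63% to between 52 / 57.5 / 59% and 42 / 53 / 57% (challenge 30 / 65 / 100 CFU/ml). At 1.5 log10 it falls to between 38 / 48 / 53% and 0 / 32 / 43%. At 0.5 log10 little changes. All of this rests on the assumed flora and on a challenge within 30-100 CFU/ml.

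This is a cheap improvement to an ancillary assay. It is not evidence that the neutralizer fails, that the main results would be biased, or that any product would gain.

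Two separate inconsistencies should be reconciled. The stated inoculum does not yield 30-100 CFU/ml. In 17.7.10 d), the wording compares Test 1 with Test 3, but the bracketed formula names Test 4; the calculations here follow the wording.

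**What to change.** Add a residual-flora control to 17.7.8.2.1, 17.7.10 and 17.7.11:

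- Section 17.7.8.2.1 states no use for the last 1.0 mL of each 6.0 mL sample. Hold it uninoculated beside the Test 1 tube and plate it on TSA+N in two parts, up to 0.5 mL within one minute and the rest at 30 minutes. Record the volume plated, since recovery from the cup may fall short of 6.0 mL.
- Report the residual count. Scale it to volume, pool it over a product's replicates, and subtract the time-matched value from Test 1 before the log transform. Matching matters: if native cells decline over 30 minutes, an early count would over-correct the later plating.
- State in advance the fraction of the Test 3 count above which a product's assay is repeated, and apply it to the pooled residual. A single plate is too noisy: 10% of 30 CFU/ml on 0.75 mL is 0.10 x 30 x 0.75 = 2.25 colonies. Pooling six 0.5 mL plates (three applications x two sites) gives 0.10 x 30 x 3.0 = 9.

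Cost: 3 products x 3 applications x 2 sites = 18 samples, or 6 subjects x 2 sides x 2 sites = 24 if every side is used. At two plates each that is 36 to 48 plates, with an occasional repeat. No extra subjects, visits or skin sampling are needed unless an assay is repeated.

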#### **17.7.8.2.2 Sampling fluid (SSF++) toxicity (Test 2)**

- a) A 5.0 mL aliquot of sampling solution will be inoculated with the challenge microorganism so that the final concentration will equal 30 – 100 CFU/ml of the challenge microorganism in the same manner as Test 1.
- b) Within one min after the addition of the challenge microorganism, the microorganisms will be enumerated by standard microbiological methods extant in the laboratory.
- c) Triplicate 0.75 mL aliquots will be removed and plated using TSA+N pour plates.
- d) After 30 minutes, the microorganisms will be enumerated a second time using the same procedures.
- e) This procedure will be repeated two times for a total of three replicates per test product per time point.

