#### **17.7.8.2.3 Test microorganism viability control (Test 3)**

- a) A 5.0 mL aliquot of PBW will be inoculated with a volume of the challenge microorganism so that the resulting suspension contains 30 – 100 CFU/ml in the same manner as Test 1.
- b) Within one min the microorganisms will be enumerated by standard microbiological methods extant in the laboratory.
- c) Triplicate 0.75 mL aliquots will be removed and plated using TSA pour plates.
- d) After 30 minutes, the microorganisms will be enumerated a second time using the same procedures.
- e) This procedure will be repeated two times for a total of three replicates per test product per time point.

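### The density, dilution and volume named for the neutralization inoculum give about 196 CFU/ml, not the 30–100 CFU/ml that the same procedure requires.

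*Combined protocol and SAP*

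**What the plan says.** All references are to Appendix 17.7 of the combined protocol and SAP.

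- **Stock and working inoculum (17.7.8.1).** A suspension is made in buffered water "and the concentration adjusted to approximately" 10^8 to 10^9 CFU/ml. Then: "Bacterial suspension will be further diluted with PBW to achieve an appropriate concentration (approximately" 10^4 CFU/ml), for use in inoculating the samples. The inoculum density is also checked by direct plating, at the start and at the finish.
- **Test 1 (17.7.8.2.1).** Of the 6.0 mL collected from a volunteer site, "5.0 mL will be transferred to a new sterile tube" and inoculated to a final 30–100 CFU/ml. A parenthesis explains how: "the prepared inoculum will be diluted using PBW to achieve the desired concentration", and "a 0.1 mL aliquot from the 10 -4 dilution will be used". Plating follows: "Triplicate 0.75 mL aliquots will be removed and plated using TSA+N pour plates".
- **Tests 2 to 4 (17.7.8.2.2 to 17.7.8.2.4).** The target is the same. Test 2 is inoculated to that level "of the challenge microorganism in the same manner as Test 1". Test 3 reads "A 5.0 mL aliquot of PBW will be inoculated with a volume of the challenge microorganism", with the volume left open but tied to 30–100 CFU/ml and to the manner of Test 1. Test 4 is worded like Test 3.
- **Acceptance (17.7.10, item g).** The 30–100 CFU/ml level has to be confirmed, and Test 3 is where this is done.

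**The concern.** The procedure fixes a density, a dilution and a volume, and also the concentration they should produce. Those four figures should agree, and they do not. The parenthesis in Test 1 also leaves unclear what the 10^-4 dilution is a dilution of: the 10^8–10^9 stock, or the working inoculum that has already been diluted.

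At stake is the validation run, not the trial result. Item g makes 30–100 CFU/ml a condition. Plates are read after 48 ± 2 hours (17.7.9), so a miss would appear only then. Test 1 uses 5.0 of the 6.0 mL collected per site, and the 1.0 mL left cannot supply another 5.0 mL test. Repeating Test 1 would therefore need fresh skin samples, in a validation planned with six subjects after a 7-day washout (17.7.3). Section 17.7.1 also chooses a low cell density on purpose, because neutralizer and toxicity effects show more readily there.

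**Working it through.** **Inputs.** Stock 10^8–10^9 CFU/ml and working inoculum about 10^4 CFU/ml (17.7.8.1); 0.1 mL added to 5.0 mL, dilution label 10^-4, target 30–100 CFU/ml, plated volume 0.75 mL (17.7.8.2.1).

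**Formula.** Final CFU/ml = inoculum density × volume added / (5.0 mL + volume added).

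**1. Trying to reproduce 30–100 CFU/ml.**

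| Reading | Density of what is added (CFU/ml) | Final CFU/ml |
|---|---|---|
| Working inoculum as named | 10^4 | 10^4 × 0.1 / 5.1 = 196 |
| 10^-4 dilution of a 10^8 stock | 10^4 | 196 |
| 10^-4 dilution of a 10^9 stock | 10^5 | 10^5 × 0.1 / 5.1 = 1,961 |
| 10^-4 dilution of the 10^4 working inoculum | 1 | 1 × 0.1 / 5.1 = 0.02 |

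The volume convention does not rescue the figure. Ignoring the added 0.1 mL gives 1,000 / 5.0 = 200 CFU/ml. Inoculating all 6.0 mL gives 1,000 / 6.1 = 164. Reading the target as colonies per 0.75 mL plate gives 196.1 × 0.75 = 147. None lies in 30–100.

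**2. Size of the miss.** 196.1 / 100 = 1.96 times the ceiling, and log10(1.96) = 0.29.

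**3. What would meet the target.**

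- Keeping 0.1 mL into 5.0 mL, the density must be 30 × 5.1 / 0.1 = 1,530 to 100 × 5.1 / 0.1 = 5,100 CFU/ml. The upper value is 1 − 5,100 / 10,000 = 49% below the named 10^4.
- Keeping the 10^-4 label, taken from the stock, the stock must be 1,530 × 10^4 = 1.53×10^7 to 5,100 × 10^4 = 5.1×10^7 CFU/ml. That is below the stated 10^8–10^9.
- Keeping 10^4 CFU/ml, the volume v solves 10^4 × v / (5 + v) = target. So v = 150 / (10,000 − 30) = 0.015 mL for 30 CFU/ml, and 500 / (10,000 − 100) = 0.0505 mL for 100 CFU/ml.

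**4. Countability.** At 196 CFU/ml a 0.75 mL plate carries about 147 colonies, against 30 × 0.75 = 22.5 to 100 × 0.75 = 75 at the target. That is still inside the 25–250 range that section 5.2.2 uses for skin samples. At 1,961 CFU/ml it would be about 1,471 colonies, well outside that range.

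**The case against.** The best defence is that the target governs and the figures are guides. Section 17.7.8.1 marks its density as approximate, Test 1 orders dilution to the desired concentration, and Tests 3 and 4 name no volume of their own. A laboratory that put 0.05 mL of a 10^4 suspension into 5.0 mL would have 500 / 5.05 = 99 CFU/ml and would meet Test 3's own text. Direct plating of the inoculum and item g are two further checks on this quantity.

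Much of this stands. A reader might infer that the validation is bound to fail item g, or that the faulty figures carry unaltered into all four tests. The documents do not support either inference. Failure follows only if the named figures are used and the instructions to hit the target are not acted on. The reference back to Test 1 points towards the same 0.1 mL, but the open volume in Tests 3 and 4 leaves room to depart from it.

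A reader might also treat every row of the table as equally likely. The 0.02 CFU/ml row is not a reading that a laboratory aiming at 30–100 would adopt. The 1,961 row conflicts with the working density of about 10^4 in 17.7.8.1, although nothing in 17.7.8.2.1 excludes it.

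What the defence does not do is make the figures agree. The parenthesis that orders dilution to the target also fixes the step, and the two cannot both be met at the stated densities. The word approximately would have to cover a reduction of about half or more. Direct plating needs incubation too, so it may give no earlier warning.

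**Conclusion.** The inconsistency is real: as named, the inoculum gives about 196 CFU/ml against a ceiling of 100, a factor of 1.96 or 0.29 log10. A stock at the upper end of its stated range, diluted 10^-4, would give about 1,960. The laboratory can reach 30–100 CFU/ml only by departing from the named density, dilution or volume. If it does not, Test 3 would be expected to exceed the limit in item g, and the validation would have to be repeated.

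The 196 rests on taking 10^4 CFU/ml at its nominal value and on complete mixing in 5.1 mL.

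Severity is low. The plan contains the means to correct or detect the error, and plates at the nominal figure remain countable. Items d to f of 17.7.10 compare tests meant to be inoculated alike, so a shared excess would largely cancel. A reader might infer a bias in the trial's efficacy results. The documents give no ground for that, because the inoculum is used only in the neutralization validation and does not enter the efficacy analysis.

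**What to change.** Reconcile the density, dilution and volume in 17.7.8.1 and 17.7.8.2.1 with 30–100 CFU/ml, and state which suspension is added. Either of these would do:

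- **Change the density.** Keep 0.1 mL into 5.0 mL and set the working inoculum in 17.7.8.1 at about 3×10^3 CFU/ml (acceptable 1.53×10^3 to 5.1×10^3). This gives 3,000 × 0.1 / 5.1 = 59 CFU/ml, or about 44 colonies per 0.75 mL plate. Replace the whole parenthesis in 17.7.8.2.1 with a statement that 0.1 mL of the working inoculum of 17.7.8.1 is added. Replacing all of it matters, since otherwise the text would still order a further dilution of a suspension already at its working density.
- **Change the volume.** Keep 10^4 CFU/ml, set the volume at 0.015 to 0.05 mL, and remove the reference to a 10^-4 dilution or state its source.

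Tests 2 to 4 then follow through their reference to Test 1. The cost is wording in two subsections, with no added subjects, samples or tests and no change to the efficacy analysis.
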